3. OBJECTIVES

We aim to test the effectiveness of the tool ('Source') and the communication skills training for health care providers.

3.1. The primary research question is:

Does the combination of the tool and the training improve observed (numerical) precision of information about treatment outcomes in clinical consultations?

3.2. The secondary research questions are:

Does the combination of tool and training affect:

- Health care providers' personalization of treatment outcome information
- Health care providers' tailoring of treatment outcome information
- Health care providers' use of visualizations
- Health care providers' setting the agenda
- Health care providers' use of time frame, initiative, treatment outcome category (on an utterance level)

- Health care providers' observed (numerical) precision of information about treatment outcomes in simulated patient consultations (effect training only)
- Health care providers' intention to inform patients about treatment outcomes using numbers (effect training only)
- Patient and physician satisfaction with communication and decision making
- Patient-reported shared decision making
- Patients' evaluation of the decision made
- Patients' evaluation and knowledge of the information provided by the health care provider
- Patients' health related quality of life
- Patients' trust in the health care provider
- Patients' anxiety
- Patients' helplessness/hopelessness
- Consultation time
- The (provisional) treatment decision made

Additionally we will assess:

- Demographical and personal variables
- Health care providers' use of the Source tool
- Health care providers' evaluation of the Source tool
- Health care providers' evaluation of the Source training + e-learning

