4. STUDY DESIGN

4.1. Design

A multi-center pragmatic cluster stepped wedge design will be adopted. All health care providers will receive the intervention, i.e. the training and tool but at different time slots. These time slots are dependent on the geographical region (see Figure 1). Before the intervention takes place, a period of four to six months (taking the holiday season into account) will be used to include patients in order to collect control measurements. The subsequent transition period, in which the intervention will take place, will take approximately three to four months. After the intervention has taken place, again a period of four to six months is scheduled in which participating health care providers will include patients for measurements. Each participating health care provider (cluster) will include approximately three patients before and three patients after the intervention has taken place. The number of three patients per care provider is used as a mean, the minimum will be set at two patients and the maximum at six. The consultation with these patients will be audio recorded and providers and patients are asked to fill in short questionnaires before and after the consultation (see paragraph 7.2). In addition, each health care provider will do one simulated patient consultation before and one after training, which will also be recorded on audio.

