5.2 Inclusion criteria

Health care providers:

- Specialist, physician assistant or nurse practitioner in the field of oncology, oncological radiotherapy or oncological surgery who are used to discussing treatment and treatment outcome with patients
- Informed consent for data collection
- Three audiorecorded treatment information consultations with oesophageal or gastric cancer patients before the scheduled transition period (control measurements)
- Three audiorecorded treatment information consultations with oesophageal or gastric cancer patients after the scheduled transition period (intervention measurements) and before the scheduled end date of the study

Patients:

- Age ≥ 18 years
- Histological or cytological proof of oesophageal or gastric cancer
- Informed consent for trial data collection

A treatment information consultation with a participating doctor to discuss either curative treatment, first line palliative treatment, and/or best supportive care.

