9. STATISTICAL ANALYSIS

9.1. Primary study parameter

Audio tapes of consultations will be analyzed, using Noldus' The Observer XT software, on the primary outcome. Time-based analysis on all utterances of information on treatment outcomes is performed. Each utterance will receive a code based on the study specific coding scheme. Utterance scores will be summarized on the level of the consultation and compared between control and intervention measurements in a within-subjects analysis. Effects with one-sided p-values < .05 will be considered significant; 95Cl's as well as effect sizes will be provided. Baseline differences across the compared patient groups on socio-demographic (age, gender, educational level, etc.) and clinical characteristics (cancer phase at time of the consultation, time since diagnosis, etc.) as well as patients' baseline measures will be examined with the appropriate statistical tests (ANOVA, Chi-squared tests). All analyses of effectiveness will be controlled for specialization of the health care provider, profession of the health care provider (specialist, fellow, nurse specialist, physician assistant) and center specific characteristics (academical or peripheral hospital, starting time of intervention).

Reasons for missing data will be registered and recorded. Dependent on the type of missing data, the appropriate procedures will be used. If necessary, multiple imputation could be applied.

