10.1.3. Patients in the trial

1. Invitation.

Eligible patients will be identified from the outpatient clinic agendas of the participating health care providers by either the health care provider, a research nurse or a research associate (depending on the logistical agreements with the individual center). If possible, the treating health care provider will be asked for permission to contact the patient. Since the role of treating health care provider is not in every case divided before consultation, this cannot always be realized.

Either the research nurse of the research associate will contact the patient by telephone, explain the study and invite to participate. We strive to allow patients at least 3 days' time to consider their participation in the study and therefore preferably contact the patient as soon as the consultation is planned. Via telephone, patients will be informed about the nature and goal of the study. Patients who consent, will be contacted by post. All subsequent (postal) contact will be arranged by the coordinating investigators in the Amsterdam UMC, location AMC.

2. Informed consent and baseline questionnaire.

After oral consent, patients will receive a written information letter with information about the study, informed consent forms and the baseline questionnaire (TO P) to be filled in at home, accompanied by a return envelope. Since time between initial contact and consultation is often short, patients will not in every case be able to fill in the informed consent forms and the baseline questionnaire before consultation. Patients will still receive a written information letter with information about the study, informed consent forms and TO P but will in this case be asked to fill these in when meeting the research associate in the waiting room for T1 P. By signing informed consent patients and their family agree to the collection of audio recording and questionnaire data.

3. Waiting room.

A research associate or research nurse will meet the patient (and their family) in the waiting room, and check for the filling in of informed consent forms as well as the baseline questionnaire. Patients will again be given the opportunity to ask questions. Patients will be informed about the procedure of recording the consultation (and the small audio recorder will be

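### The effectiveness analyses adjust only for provider and centre characteristics; the patient's cancer phase, which can differ between periods, is tested for imbalance but left out of the effect model

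*Protocol*

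**What the plan says.** Protocol section 9.1 sets the primary comparison as control versus intervention consultations in a within-subjects analysis, judged at one-sided p < .05. It then states the covariates: "All analyses of effectiveness will be controlled for specialization of the health care provider, profession of the health care provider", together with "center specific characteristics (academical or peripheral hospital, starting time of intervention". No patient variable is among them.

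Cancer phase appears one sentence earlier, among the "clinical characteristics (cancer phase at time of the consultation, time since diagnosis, etc" whose differences between the patient groups "will be examined with the appropriate statistical tests (ANOVA, Chi-squared tests". Patients' baseline measures are treated in the same way. The section does not say what follows if a difference is found. Section 9.2 analyses the consultation-based secondary outcomes as in 9.1.

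Three other places bear on this:

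- Section 4.1: each provider "will include approximately three patients before and three patients after the intervention has taken place", so the two periods contain different patients.
- Section 5.2: the consultation may be one "to discuss either curative treatment, first line palliative treatment, and/or best supportive care".
- Section 10.1.3: "Eligible patients will be identified from the outpatient clinic agendas of the participating health care providers by either the health care provider". Where the provider does not do this, nursing or study staff do; the arrangement varies by centre.

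**The concern.** Each provider is compared with themselves, before and after training. Specialization, profession, hospital type and starting time normally take one value per provider, so they cannot explain a difference between that provider's two periods. What can differ within a provider is the patients.

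How numerically outcomes are discussed plausibly depends on whether the disease is potentially curable or metastatic. Section 6.1 describes separate outcome data for these settings. If the mix of settings shifts systematically between periods, part of the estimated intervention effect is really a case-mix effect, and the stated covariates cannot remove it.

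The design leaves room for such a shift. Control consultations always come before intervention consultations for a given provider, so period is not randomized within provider. Providers know whether they have been trained, and in some centres they may identify the patients.

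The planned baseline tests do not fill the gap. A significance test corrects nothing in the effect estimate, and with this sample it has little power to detect a moderate shift.

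**Working it through.** **The plan's own figure.** Section 5.4 gives an effect of 0.5 SD, an intracluster correlation of 0, 80% power and 21 providers with 3 + 3 patients. For two means, n per period = 2 × (1.960 + 0.842)² / 0.5² = 62.8, so 63 per period, 126 in total and 21 × 6. The stated 126 is reproduced with a two-sided 5% level. It is used here only for the 63 per period; the error rates below use the one-sided 5% level of section 9.1.

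**Assumed inputs (not in the protocol).** Phase mix 50/50; phase effect on the primary outcome 0.25, 0.5 or 1.0 SD; systematic shift in phase mix of 10 percentage points between periods.

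**Shift in the estimate and in the error rate.**

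- Shift in the estimate = phase effect × difference in phase share.
- Standard error of the contrast = √(2/63) = 0.178 SD.
- One-sided error rate = P(Z > 1.645 − shift/0.178).

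| Phase effect (SD) | Shift in estimate (SD) | Share of 0.5 SD target | One-sided error rate |
|---|---|---|---|
| 0.25 | 0.25 × 0.10 = 0.025 | 5% | 6.6% |
| 0.5 | 0.5 × 0.10 = 0.05 | 10% | 8.6% |
| 1.0 | 1.0 × 0.10 = 0.10 | 20% | 13.9% |

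A larger assumed shift, from 50% to 65% with a phase effect of 0.5 SD, gives 0.075 SD (15% of the target) and an error rate of 11.0%.

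**Power of the baseline test.** For two proportions near 50%, with 63 per period, the standard error of the difference is √(2 × 0.25/63) = 0.089. A two-sided 5% test then has power of about 20% at 10 points, 50% at 17.5 points and 61% at 20 points.

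**Do the listed covariates help?** Two simulations with a true effect of 0 and a phase effect of 0.5 SD give the mean estimates below. The 10-point runs used 8,000 trials, an assumed provider ICC of 0.1 and randomly assigned provider and centre covariates. The 15-point run used 2,000 trials, with specialization and hospital type as the covariates.

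| Scenario | Unadjusted | Provider/centre covariates | Phase added |
|---|---|---|---|
| 10-point shift, 3 + 3 patients | 0.052 | 0.052 | 0.002 |
| 10-point shift, 2 to 6 patients per period | 0.049 | 0.049 | −0.002 |
| 15-point shift, 3 + 3 patients | 0.073 | 0.073 | −0.004 |

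With balanced data the listed covariates changed the estimate by nothing beyond rounding error. With 2 to 6 patients per period and no provider effects in the model, they moved single estimates by 0.027 SD on average but left the mean shift where it was.

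**Chance imbalance.** The 0.089 is also the SD of a purely random difference in phase share, so differences up to about 1.96 × 0.089 = 0.17 are expected by chance. That is noise already contained in the standard error, not bias. Adjusting for phase reduces it only modestly: the SD of the estimate fell from 0.175 to 0.171.

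**The case against.** Section 9.1 names covariates but does not say that no others will be added, and patient-level covariates are often settled in an SAP, which is not at hand. An SAP could add phase. But this protocol does not leave the matter open: it states a set for all effectiveness analyses, and that set can be judged as stated.

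No documented figure shows a bias. The phase mix, the phase effect and the shift are all assumed, and with no systematic shift the bias is zero. The 13.9% needs a phase effect twice the trial's target effect. This stands, and the error rates should be read as conditional, not expected.

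The selection route is partial. Sections 1 and 5.1 have all eligible patients approached, a nurse or associate makes the telephone contact, and the treating provider is not always known beforehand. This lowers the likelihood of a shift. It does not exclude one, because providers may identify patients in some centres, are asked for permission where possible, and only 50% of those approached are expected to take part.

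Phase probably clusters by specialty, while the simulations made it independent of provider. A provider with a uniform caseload has little room for a shift. This also stands, and it dilutes the effect. If, for example, only half the providers had mixed caseloads and shifted by 10 points, the average shift would be 5 points, and at 0.5 SD the estimate would move by 0.5 × 0.05 = 0.025 SD.

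Finally, section 7.2.1 does not say which instruments are given before the consultation, so the outcomes with a usable baseline score cannot be listed from the protocol.

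**Conclusion.** The concern holds. The covariates fixed in section 9.1 cannot correct the before-versus-after contrast for a change in patient mix. The one patient characteristic most likely to matter is only put through a low-powered test with no stated consequence. Under the assumed 50/50 mix and systematic 10-point shift, the estimate moves by 0.025 to 0.10 SD and the one-sided error rate rises from 5% to between 6.6% and 13.9%, for phase effects of 0.25 to 1.0 SD. The direction and size of any real shift cannot be known from the protocol, and clustering of phase by specialty would make it smaller. This is a change that should be made because it is cheap and closes a real gap. It is not evidence that the result will be biased, and the sample size of 126 is unaffected.

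**What to change.** In section 9.1, prespecify disease setting (for example potentially curable versus metastatic or palliative) as a covariate in the primary and secondary effect models for patient consultations, whatever the baseline comparison shows. This also avoids choosing covariates after seeing the data.

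Code the setting from information available before the consultation, not from the treatment discussed or chosen. Section 3.2 lists "The (provisional) treatment decision made" as an outcome, and the consultation categories in section 5.2 can overlap.

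For outcomes that have a pre-consultation patient score, add that score to the model and name those outcomes. Report baseline characteristics descriptively by period instead of testing them.

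Add disease setting, with its source, to the patient variables in section 7.1.5, which lists tumour location but not phase. The provider and centre covariates may stay, but should not be relied on to control case mix.

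The cost is one or two model parameters, one line in section 7.1.5 and a coding rule, with no extra patients or visits.

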9.2. Secondary study parameters

The secondary outcomes based on the consultation, both on the level of the utterance or the level of the consultation) will be coded likewise by the study specific coding scheme. Effects of the intervention on the outcomes will be analyzed in the same manner as the effect on the primary outcome (see 9.1).

The effect on the secondary outcomes measured by patient or health care provider self-report will be analyzed in multi-level regression analysis.

The effect of the training on the observed (numerical) precision of information about outcomes of treatment in simulated patient encounters will be assessed by using a repeated measure ANOVA. To answer questions regarding the evaluation of the intervention (tool and training), the appropriate descriptive statistics will be used (medians, percentages).

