5.4 Sample size calculation

The intervention is considered successful if a significant difference is observed in the precision of information about treatment outcomes provided by the health care providers (primary outcome) before and after the intervention. Assuming a medium sized effect (0.5 SD), an intracluster correlation of 0 and a power of 80%, 21 health care provider , i.e. clusters, are needed with 6 patients per health care provider (3 control and 3 post intervention). Thus, in total 21 health care providers and 126 patients need to be included in the study. Based on a predicted response rate of 50 % 252 patients will be approached.

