7.2. Study procedures

7.2.1. Patient study procedures

Patients with oesophageal or gastric cancer who are scheduled for a treatment information consultation, will be approached by telephone for informed consent by a SOURCE research employee. Informed consent forms together with the information letter and the baseline TO questionnaire will be sent to the patient by mail or email.

Consenting patients will be asked to fill in a questionnaire at home before the start of the consultation (T0 P; 7-15 minutes) and one in the waiting room, just before the start of the consultation (T1 P; 3-5 minutes).

Together with receiving T1, patients will receive an envelope containing the T2 questionnaire (10-20 minutes). Patients will be asked to fill in the T2 questionnaire within a time period of two weeks after the consultation. The treatment information consultation will be audio recorded. Dependent on the procedures as agreed upon with the participating centers, either the research nurse of the participating center or a researcher of the SOURCE study will facilitate the audiorecording and questionnaire completion.

Three months after the consultation, patients will be asked to fill in the last questionnaire (T3 P; 10-15 minutes). Patients participating in the POCOP trial will not receive this questionnaire. For these patients, the data from the T2 questionnaire will be acquired through the POCOP database.

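### Section 9.1 adjusts only for provider and centre and merely tests patients' baseline measures; a self-reported scale with a pre-consultation score should be adjusted for that score

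*Protocol*

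**What the plan says.** Three parts of the Protocol bear on this point.

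- **The model.** Section 9.2: "The effect on the secondary outcomes measured by patient or health care provider self-report will be analyzed in multi-level regression analysis". It names no covariates.
- **The adjustment set.** Section 9.1 lists the variables that all effectiveness analyses will control for: the provider's specialty and profession, the type of hospital, and when the intervention started. None belongs to the patient.
- **The use of baseline data.** In section 9.1, alongside socio-demographic and clinical characteristics, "patients' baseline measures will be examined with the appropriate statistical tests", with ANOVA and chi-squared tests as the examples. No consequence of a significant or non-significant result is given.

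On design, section 4.1 says that each provider "will include approximately three patients before and three patients after the intervention has taken place". On data, section 7.2.1 says that "the baseline TO questionnaire will be sent to the patient by mail or email" (this is T0), and a short T1 questionnaire follows in the waiting room. Section 7.1.4 lists the patient scales, among them EORTC QLQ-C30 and OG25, STAI and (Mini-)MAC, without time points. The instruments in T0 and T1 are not listed anywhere.

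**The concern.** A provider's control patients and intervention patients are different individuals. Comparing phases within a provider removes stable differences between providers, but not the spread between patients in a scale such as quality of life or anxiety. Where the same scale was completed before the consultation, the patient's own earlier score is likely to be among the best predictors of the later one. The stated adjustment set does not use it.

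Two things are at stake. The intervals for these outcomes are wider than they need to be. In addition, if patients in one phase start better or worse off, part of that difference appears as an effect of the tool and training. The phases are separated in calendar time, and the population mixes curative, first-line palliative and best supportive care consultations (section 5.2), so a difference need not arise by chance alone. Testing baseline measures for significance does not protect against this. With about 63 patients per phase, such a test often misses a difference large enough to matter, and nothing is said about what follows if it does not.

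**Working it through.** **Inputs.** Section 5.4 gives an effect of 0.5 SD, an intracluster correlation of 0, power of 80%, and three control plus three intervention patients for each of 21 providers: "in total 21 health care providers and 126 patients need to be included in the study". That is 21 × 3 = 63 per phase. These planning values were set for the primary outcome and are borrowed here as a scale. The correlation r between a patient's pre-consultation score and the outcome is not in the Protocol; it is assumed over 0.3 to 0.7.

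**Step 1: reproduce the planned size.** n per phase = 2(z₀.₉₇₅ + z₀.₈₀)² / 0.5² = 2(1.960 + 0.842)² / 0.25 = 62.8, so 63 per phase and 126 in total. This matches with a two-sided 5% test. A one-sided 5% test would need 50 per phase. Section 9.1 says "Effects with one-sided p-values < .05 will be considered significant"; that mismatch is a separate matter and does not alter this point.

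**Step 2: standard error without adjustment.** In SD units, SE = √(2/63) = 0.178. This is also the chance SE of a baseline difference between phases.

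**Step 3: with the patient's own pre-score as covariate.** Residual variance is multiplied by 1 − r², so SE = 0.178 × √(1 − r²). Power at 0.5 SD (two-sided 5%) = Φ(0.5/SE − 1.96). The difference detectable with 80% power is 2.80 × SE.

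| r | 1 − r² | SE (SD) | Power at 0.5 SD | Detectable difference (SD) |
|---|---|---|---|---|
| no adjustment | 1.00 | 0.178 | 80.1% | 0.50 |
| 0.3 | 0.91 | 0.170 | 83.7% | 0.48 |
| 0.5 | 0.75 | 0.154 | 90.0% | 0.43 |
| 0.7 | 0.51 | 0.127 | 97.6% | 0.36 |

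Residual variance falls by 9%, 25% and 51%, and the SE by about 5% to 29%.

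**Step 4: carry-over of a baseline difference.** The expected shift in the unadjusted effect is r × imbalance. An imbalance of 0.3 SD gives 0.3 × 0.3 = 0.09, 0.5 × 0.3 = 0.15 and 0.7 × 0.3 = 0.21 SD. An imbalance of 0.2 SD gives 0.06, 0.10 and 0.14 SD.

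**Step 5: would the baseline test notice?** Power = Φ(imbalance/0.178 − 1.96). For 0.2 SD: Φ(1.12 − 1.96) = 20%. For 0.3 SD: Φ(1.68 − 1.96) = 39%. An imbalance of 0.3 SD is therefore more likely to pass unflagged than to be flagged.

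**The case against.** The strongest reply is that section 9.2 is silent rather than wrong. Multi-level regression could nest repeated questionnaires within patients and so already use the earlier score, and detailed covariates for secondary models are commonly left to a statistical analysis plan, which is not at hand. A reader might infer that the Protocol rules out baseline adjustment; it does not say that. What remains is that 9.1 is not silent. It states an adjustment set for all effectiveness analyses, that set contains nothing about the patient, and it gives baseline measures one use only.

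Second, a reader might infer that quality of life, anxiety and helplessness are measured at T0. The Protocol does not support that as fact, because neither the contents of T0 and T1 nor the time points of the scales are given. The baseline measures in 9.1 could be the items in section 7.1.5, such as information need or experience with graphs and numbers. Satisfaction, SDMQ-9 and decisional conflict concern the consultation or the decision and may have no pre-score. This objection stands, and it makes the point conditional.

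Third, the size rests on an assumed correlation. At r = 0.3 the gain in precision is small. The 63 per phase is a recruitment target with full questionnaire return, clustering is ignored, and the imbalances are hypothetical. Because each provider contributes to both phases, stable case mix at provider level cancels, and specialty and hospital type may carry some information on patient type. All of this limits the size of the problem without reversing its direction. An unadjusted model is also not invalid under chance imbalance; it is less precise.

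**Conclusion.** The point holds in conditional form. For any patient-reported secondary outcome with a T0 or T1 score, the adjustment rule in 9.1 leaves out the patient's own starting value, and a significance test of imbalance does not replace it. With 63 per phase, an intracluster correlation of 0 and r between 0.3 and 0.7, the SE could fall from 0.178 SD to between 0.170 and 0.127 SD. Without adjustment, a 0.3 SD baseline difference would bring in 0.09 to 0.21 SD, against a planning effect of 0.5 SD. If a scale has no pre-consultation score, the point does not apply to it.

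A reader might extend this to the trial's main conclusion. That is not supported: the primary outcome is coded from the audio recording, and neither the success criterion nor the sample size in 5.4 depends on these models. The change is worth making because it costs very little, not because the trial is at risk without it.

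**What to change.** In section 9.2, state that every patient-reported outcome also measured at T0 or T1 is analysed in the multi-level model with the patient's own pre-consultation score as a covariate, in addition to the 9.1 list and regardless of what the baseline tests show. List which scales T0 and T1 contain, so that it is clear where the rule applies. Keep the baseline comparison in 9.1 as description only.

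Section 10.1.3 accepts that some patients cannot complete T0 at home and are asked to do so in the waiting room. That score still precedes the consultation and can be used. Where a pre-score is missing, use the multiple imputation that 9.1 already allows. Simple single imputation of a baseline covariate is less safe here, because control and intervention patients are not randomised groups.

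The cost is a few lines of text and slightly more analysis work. No new data are needed for scales already in T0 or T1, and the rule asks for none where a scale is not.
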